4.3 Rescreening

Rescreening will be allowed in patients initially excluded for these criteria:

1. Fracture less than 3 months of screening. These patients can be rescreened after radiologically documented healing of fracture. If individual sustains fracture in the period after the screening visit but before the day 1 of the trial, rescreening will be allowed after 3 months from the date of the fracture.
2. Vitamin D < 15 ng/dL; rescreening for vitamin D levels will be allowed after supplementation.
3. Serum albumin-corrected calcium levels below 8 mg/dL; rescreening will be allowed after calcium supplementation.
4. Current clinically significant infection; rescreening will be allowed after resolution of infection.
5. Platelet count less than 75,000/mm³. Rescreening with a second CBC will be allowed.

4.4 Recruitment of Participants

Recruitment will occur through the clinical practices of each site investigator, through the RDCRN Contact Registry, and, as needed, via mailings to appropriate clinicians in the investigators' catchment areas and to the patient members of the Osteogenesis Imperfecta Foundation.

Recruitment will occur by physicians, study nurses, and research coordinators. Details of the goals of the research and the risk and benefits of the protocol will be reviewed with each potential study participant. Strict patient confidentiality will be observed throughout all aspects of the study. Potential subjects may be requested to provide medical records prior to consenting to the study to establish eligibility. In this case a medical records release form will be completed to request clinical lab results such as genetic confirmation data and historical X-rays. While medical records will be reviewed by members of the research team, no individually identifiable patient data will be distributed to non-research or care-giving team members.

4.5 Retention Strategies

OI is a rare disorder that is managed by a small number of specialists. Most of these specialists work regularly with the OIF, participate in scientific and clinical research meetings and have the expertise to provide medical and surgical care to individuals with OI. These clinical relationships provide an avenue for increased communication that can facilitate retention. Furthermore, this study may provide benefit to the participants that would enhance retention. Nurses/genetic counselors/clinical research coordinators at each site will work to maintain close contact with participants, including regular clinic visits, newsletters and communication by phone, email and web sites. Study related testing for this research protocol will be performed at no charge to the participant. Finally, we will reimburse families for some travel related costs.

4.6 Investigational Product(s)

Fresolimumab will be supplied as a sterile lyophilized powder for reconstitution. The sterile lyophilized powder is intended to be reconstituted with 5.1 mL (50 mg vial) sterile Water for Injection (sWFI). For the vials containing fresolimumab this will result in a protein concentration of approximately 10 mg/mL in a 50 mM sodium phosphate buffer at pH 7.1, containing 25 mM sodium chloride, 3% mannitol, 1% sucrose, and 0.01% Polysorbate-80.

Packaging

Packaging and distribution services will be coordinated by the Sponsor or its designee for all study sites. Fresolimumab is stored in clear glass vials of 5 mL capacity (nominal), which meet the USP standard for Type I glass, closed by a siliconized butyl rubber stopper. Each vial contains approximately 50 mg of IP. All label text will comply with country specific regulatory requirements.

Storage

Upon receipt by the clinical site, IP must be stored at 2 to 8°C (35.6 to 46.4 °F), in a limited-access area until preparation for infusion. Reconstituted fresolimumab is stable for up to 24 hours after reconstitution with sWFI at either room temperature or under refrigeration (between 2 to 8° C or 35.6 to 46.4° F). Although stable for up to 24 hours under these conditions, fresolimumab in sWFI should be used immediately. All used and unused vials should be stored and organized in a secure area for later drug accountability.

4.7 Single Dose Administration Study (Stage 1)

Primary objective

1. Pharmacokinetics of fresolimumab with a single dose administration
2. To evaluate the safety of a single dose administration of fresolimumab in adults with moderate-to-severe OI with respect to:
 - Vital signs - heart rate, blood pressure, respiratory rate, and body temperature.
 - Laboratory variables.
 - EKG (Corrected QT interval).
 - Adverse events and serious adverse events.

Secondary Objectives

Effect of fresolimumab with respect to:

- Markers of bone turnover in blood (type 1 procollagen, N-terminal or P1NP, Osteocalcin or Ocn, and C-terminal telopeptide or CTX).
- Areal bone mineral density (aBMD) at the hip or the lumbar spine as measured by dual-energy X-ray absorptiometry (DXA) scan.

Dose

- 4 subjects will receive a single intravenous infusion of fresolimumab at a dose of 1 mg/kg body weight. Maximal body weight used for calculation of the drug dose

is 80 kg; for those weighing greater than 80 kg, the drug dose will be calculated using a weight of 80 kg. Total duration of study participation per subject is 6 months.

- 4 subjects will receive a single intravenous infusion of fresolimumab at a dose of 4 mg/kg body weight. Maximal body weight for calculation of the drug dose is 80 kg; for those weighing greater than 80 kg, the drug dose will be calculated using a weight of 80 kg. Total duration of study participation per subject is 6 months.

The two doses have been selected based on safety data from previous studies conducted with fresolimumab that have shown that single doses up to 4 mg/kg have been well tolerated.

Study Procedures

This study will require six visits at a participating clinical site of the BBD consortium. Laboratory tests, ECGs, and radiographs obtained during this study will be interpreted locally by the PIs.

A patient can be enrolled in the study only after an in-person screening visit which will be conducted at BCM. Day 1 visit, during which the participant will receive the study medication will have to be an in-person visit at BCM. Participants are expected to come in for the follow up visits to the study site at BCM. However if there are unforeseen circumstances, or safety reasons (e.g., COVID-19) due to which a participant is unable to travel to BCM, for the follow up visits, an attempt will be made to accommodate study procedures virtually and/or at a remote site which is close to the place of the residence.

Screening visit procedures

- Obtain informed consent.
- Record medical history.
- Determine if participant has used or is using an exclusionary medication.
- Determine if participant plans to have invasive dental work or skeletal surgery during the period of the study.
- Perform physical examination.
- Measure vital signs - heart rate, blood pressure, respiratory rate, and body temperature.
- Measure height and weight.
- Collect blood sample for laboratory tests (Safety: comprehensive metabolic panel (CMP), complete blood count (CBC), PT/INR, vitamin D testing, bone remodeling markers [serum C-terminal telopeptide of type 1 collagen (CTX), Osteocalcin (Ocn), and amino-terminal propeptide of type I collagen (P1NP)], and lymphoblast culture).
- Confirm that the subject has a genetic test demonstrating that s/he has a Glycine substitution in *COL1A1* or *COL1A2*, or pathogenic variants in *CRTAP*, *PPIB*, or *LEPRE1*. If not present, collect sample for DNA testing.
- Collect urine sample for laboratory test (Safety: urinalysis OR urine dipstick, urine pregnancy test for women of child-bearing age).
- Perform skeletal survey (if historical x-rays are not available to review and ascertain the bony deformities or scoliosis).
- Perform a 12-lead EKG.

- Perform tuberculosis screening by a positive purified protein derivative (PPD) test or Interferon-gamma release assay.

Prior to enrollment (Day 1) screening eligibility criteria for each subject will be reviewed by participating investigators. Individuals who meet the criteria for enrollment will have Study Visit 1 within 60 days of screening.

Day 1 visit procedures (Baseline)

- Review and confirm that the subject meets all criteria for inclusion.
- Confirm that the subject would not be excluded based on screening laboratory tests, a clinically significant infection, a recent fracture or use of any medications since the screening visit that would exclude them from participation.
- Measure vital signs - heart rate, blood pressure, respiratory rate, and body temperature.
- Collect urine from female subjects to determine pregnancy status.
- Perform DXA scan of the lumbar spine (test may not be performed if there is significant scoliosis or the patient has had spinal instrumentation).
- Perform DXA scan total hip and femoral neck (test may not be performed if there are pins or rods in the region of interest).
- Collect blood for pharmacokinetics prior to infusion of fresolimumab
- Intravenous Infusion of fresolimumab over 30 minutes.
- Collect blood for pharmacokinetics after the end of the infusion.
- Subjects will be monitored for three hours for any infusion-related reactions (document adverse events) and will be discharged home.

Day 15 visit procedures

- Perform a physical exam.
- Measure vital signs - heart rate, blood pressure, respiratory rate, and body temperature.
- Record adverse events assessment including history of any oral or mucosal bleeding.
- Perform a 12-lead EKG.
- Collect blood for laboratory tests (Safety: CBC, CMP, PT/INR; Pharmacokinetics; Lymphoblast culture).
- Collect urine sample for laboratory test (Safety: urinalysis OR urine dipstick).
- Document adverse events.

Day 30 visit procedures

- Perform a physical exam.
- Measure vital signs - heart rate, blood pressure, respiratory rate, and body temperature.
- Collect blood for laboratory tests (Safety: CBC, CMP, PT/INR; Pharmacokinetics; Bone remodeling markers).
- Collect urine sample for laboratory test (Safety: urinalysis OR urine dipstick).
- Record adverse events assessment including history of any oral or

mucosal bleeding.

Day 90 visit procedures

- Perform a physical exam.
- Measure vital signs - heart rate, blood pressure, respiratory rate, and body temperature.
- Record medical history.
- Collect blood for laboratory tests (Safety: CBC, CMP, PT/INR; Pharmacokinetics; Bone remodeling markers).
- Collect urine sample for laboratory test (Safety: urinalysis OR urine dipstick).
- Document adverse events.

Day 180 visit procedures

- Perform a physical exam.
- Measure vital signs - heart rate, blood pressure, respiratory rate, and body temperature.
- Record adverse events.
- Collect blood for laboratory tests (Safety: CBC, CMP, PT/INR; Pharmacokinetics; Bone remodeling markers).
- Collect urine sample for laboratory test (Safety: urinalysis OR urine dipstick)
- Perform a 12-lead EKG.
- Perform DXA scan of the lumbar spine (test may not be performed if there is significant scoliosis or the patient has had spinal instrumentation).
- Perform DXA scan total hip and femoral neck (test may not be performed if there are pins or rods in the region of interest).
- Document adverse events.

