- Collect urine sample for laboratory test (Safety: urinalysis OR urine dipstick, urine pregnancy test for women of child-bearing age.)
- Perform a 12-lead EKG
- Perform DXA scan of the lumbar spine (test may not be performed if there is significant scoliosis or the patient has had spinal instrumentation)
- Perform DXA scan total hip and femoral neck (test may not be performed if there are pins or rods in the region of interest)
- Perform a peripheral QCT
- Perform a pulmonary function test
- Perform a 6-minute walk test
- Document adverse events.

- Subjects' participation will conclude when they are discharged home following this visit.

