4.9 Data Elements

Once referred for screening, the participant's diagnostic testing will be reviewed to assure that the correct OI classification has been made and eligibility requirements are met based on study inclusion and exclusion criteria. Data will be collected at study visits per the **Schedule of Events for each study group**. We will use a variety of methods to obtain these data. Certain information will be obtained from a historical review of existing charts and laboratory/treatment data. Other data will be obtained from patients or their families through a standard interview, examination or laboratory/functional testing. The investigators who will perform functional assessments and other critical evaluations will be included as investigators on their local institution's IRB application.

Medical History: Medical history will be recorded on a history and physical examination form.

12-lead EKG: EKG at the screening visit then at 2 subsequent study visits for all study participants.

Bone mineral density: A dual-energy x-ray absorptiometry (DXA) at the lumbar spine, total hip and femoral neck will be performed.

X-rays of the spine: Standard posterio-anterior and lateral views will be taken, preferably in the standing position. If this is not possible, these radiographs will be obtained in the sitting position. If participants not able to sit, the X-rays will be taken in the supine position. Taking each of the two views on a single film (skull base to sacrum) is preferred. All radiographic images will be reviewed at the screening visit to determine eligibility. Historical surveys are acceptable if X-rays taken demonstrate the boney abnormalities that are required as inclusion criteria.

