Peripheral Quantitative CT of the forearm: A peripheral quantitative CT (pQCT) will be performed at Baseline and exit visits for those subjects participating in the 2nd stage of the study to determine bone mineral density. Measurements will be performed at the non-dominant forearm. In case of recent fracture (< 2 years before) or the presence of metal at this measurement site, the contralateral forearm will be used. Two sites at the forearm will be analyzed, the metaphysis ('4% site') and the diaphysis ('65% site'). Trabecular bone is analyzed at the 4% site, cortical bone is analyzed at the 65% site. The main outcome measures of these analyses are trabecular volumetric bone mineral density (vBMD, 4% site), cortical vBMD (65% site), bone mineral content (both sites) and section modulus (a measure of bone strength, 65% site).

Pulmonary function tests: These will be performed in participants enrolled in the 2nd stage of the study at baseline and exit visits, according to the American Thoracic Society guidelines. Lung volume measurements will be determined by helium dilution. Arm span will be measured to obtain a corrected height and will be used for calculating predicted lung volumes and flow rates. Vital capacity (VC), residual volume (RV), total

lung capacity (TLC), forced vital capacity (FVC), forced expiratory volume in 1 second (FEV1), and FEV1/FVC will be calculated for each participant to determine whether participants suffer from pulmonary compromise due to an underlying tissue disorder, which may go unrecognized without PFT, or if scoliosis is the actual cause for pulmonary compromise. Restrictive lung disease will be defined as a reduction in the VC and a ratio of FEV1/FVC greater than or equal to 80%. Obstructive lung disease will be defined as a reduction in FEV1 and a ratio of FEV1/FVC less than 80%⁸.

6 Minute Walk Test: A 6 minute walk test will be performed at the baseline and exit visits for those subjects enrolled in the 2nd stage of the study to determine the subject's mobility.

Numeric Rating Scale: Pain will be evaluated using the Numeric Rating Scale (NRS). This is a self-report assessment scale for patients who are able to use numbers to rate the intensity of their pain.

PROMIS® 29: This tool will be assessed at the screening, day 180 and day 360 study visits for participants enrolled in the 2nd stage of the study.

All study elements are interpreted locally by the respective PIs.

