5.10 Quality Control: Study Related Procedures

Accurate, consistent and reliable data will be ensured through the use of standard practices and procedures. The DMCC will audit the Investigators' source data against eCRF entries and verify that the data are accurate.

6. Statistical Considerations

This study is designed to assess the safety and tolerability of fresolimumab in patients with Osteogenesis Imperfecta.

Sample Size: No formal sample size calculations were done for this study. The sample size was selected to allow for an initial assessment of safety in this population and dose range and feasibility of enrollment in this rare disorder. The sample size is 8 for the single dose study and 8 for the repeat dose study. The overall enrollment will be 16.

If needed, 2 additional patients will be enrolled in the repeat dose study to account for a drop-out rate of 20%.

Treatment-Related Adverse Events will be summarized by dose groups. Changes in vital signs, EKG, shifts in laboratory assessments and physical examinations, and patient-reported symptoms will be described. These will assess the primary endpoint of safety. Percent change in bone remodeling markers will be analyzed using a mixed model. BMD in the lumbar spine and the hip at 6 months for single dose study and 12 months for the multiple dose study will be compared to pretreatment levels using a Wilcoxon Signed Rank test. Percent change in the variables of the pulmonary function tests, and change in the 6-minute walk tests, and Numeric Rating Scale (NRS) for pain will be evaluated by Wilcoxon Signed Rank test. Values for derived pharmacokinetic variables, including Cmax, area under the curve, distribution, half-life (T1/2a), elimination half-life (T1/2b), clearance (CL), and volume of distribution at steady state (Vss), will be calculated as previously described and summarized by dose-group using descriptive statistics.

7. Data Management

The results from Screening and data collected during the study will be recorded in the

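### The only post-baseline DXA may move to a remote scanner with no same-device or cross-calibration rule, so a relocated participant's BMD change mixes treatment effect with scanner difference

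*Combined protocol and SAP*

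**What the plan says.** Both stages treat Day 1 and the follow-up visits differently (sections 4.7 and 4.8, Study Procedures). On Day 1 the rule is strict: "Day 1 visit, during which the participant will receive the study medication will have to be an in-person visit at BCM". For later visits there is an expectation and an exception. The expectation is "Participants are expected to come in for the follow up visits to the study site at BCM". The exception covers unforeseen circumstances or safety reasons, in which case "an attempt will be made to accommodate study procedures virtually and/or at a remote site which is close to the place of the residence". No procedure is exempted from it.

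The visit lists place baseline DXA on Day 1 in both stages, with pQCT and lung function added in Stage 2. Each is repeated once, at Day 180 (Stage 1) or Day 360 (Stage 2). Neither exit visit includes an infusion.

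On method, section 4.9 says "A dual-energy x-ray absorptiometry (DXA) at the lumbar spine, total hip and femoral neck will be performed", which names skeletal sites but no device. For pQCT it specifies which forearm to measure, again without a device. Lung function follows American Thoracic Society guidelines. On reading, "All study elements are interpreted locally by the respective PIs". The schedule footnotes and sections 5.9 and 5.10 contain no device, phantom, cross-calibration or central-reading rule.

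Section 6 then says that lumbar spine and hip BMD at 6 or 12 months "will be compared to pretreatment levels using a Wilcoxon Signed Rank test". It has no scanner term and no rule for a scan from another machine. It does not say whether the test is run per group or pooled, and it states no significance level.

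**The concern.** A paired before-and-after comparison assumes that the measuring instrument stays the same. Here the baseline is tied to one site, while the only later measurement may be taken near the participant's home. There is no untreated group in which a scanner shift would show up, so a relocated participant's BMD difference cannot be divided into a treatment part and a machine part.

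BMD is a named secondary outcome in both stages, and section 8.2 cites it, with biochemical markers, as the evidence of benefit on bone. With 8 participants per stage and 4 per group, each pair carries much weight. The numbers may fall further, since spine scans can be skipped for scoliosis or instrumentation and hip scans for pins or rods.

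The deviation list in section 7.5 adds to the problem. A procedure outside its window is a named deviation; a change of device is not. A late scan on the right machine is flagged, while an on-time scan on another machine may go unrecorded and then cannot be corrected later.

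**Working it through.** **The plan's own figure.** Section 6 gives no effect size, SD, power or level for BMD. The only figure that can be derived is the Stage 2 dropout allowance: 8 / (1 − 0.20) = 10, so 2 additional participants. It reproduces, and it has no bearing on the device question.

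**Inputs from the documents.** 8 participants per stage, 4 per group; one baseline and one exit DXA; a paired signed-rank test.

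**Assumed inputs.** Scanner offset 1–5%; SD of the paired percent change 2% or 3%; true change 0% or 3%; two-sided 5% level; all 8 pooled within a stage unless stated. The plan does not say that BMD is analysed as percent change; that scale is used here for illustration.

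**Step 1: shift in the mean.** Shift = offset × (remote scans / n).

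- One remote of 8: 1%/8 = 0.125 to 5%/8 = 0.625, that is 0.13–0.63 points.
- One remote of 4: 1%/4 = 0.25 to 5%/4 = 1.25 points.
- Two remote of 8: 0.25–1.25 points. Four of 8: 0.5–2.5 points.

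**Step 2: what the exact test can do.** Let W be the smaller signed-rank sum.

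- n = 8: five sign patterns give a rank sum of 3 or less, so p = 2 × 5/2⁸ = 0.039. Seven give 4 or less, so p = 2 × 7/2⁸ = 0.055. Rejection needs W ≤ 3.
- n = 7: rejection needs W ≤ 2, p = 2 × 3/2⁷ = 0.047.
- n = 4: the smallest possible p is 2/2⁴ = 0.125. A test per group cannot reach 5%, so there the damage is to the estimate only.

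**Step 3: type I error at n = 8, no true change.** With one remote scan it stays at 0.039 whatever the offset. The other seven signs are fair coins, and the rejection region is symmetric, so for any rank of the shifted pair the chance of rejection is the same whether its sign is plus or minus. With several remote scans and a common 2% offset, simulation gives:

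| Remote scans | SD 2% | SD 3% |
|---|---|---|
| 0 or 1 of 8 | 0.039 | 0.039 |
| 2 of 8 | about 0.055 | 0.047 |
| 4 of 8 | 0.133 | 0.088 |

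If offsets instead vary independently between remote scanners around zero, type I error stays near 0.039.

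**Step 4: power for an assumed true 3% change, n = 8.**

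| Situation | SD 2% | SD 3% |
|---|---|---|
| No remote scan | 0.92 | 0.61 |
| One remote, opposing 1% offset | 0.89 | 0.57 |
| One remote, opposing 2% offset | 0.83 | 0.51 |
| One remote, opposing 5% offset | about 0.47 | 0.30 |
| Remote pair dropped (n = 7) | 0.88 | 0.57 |

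With independently varying offsets (SD of offset 2%, SD of change 2%), power is 0.85 with 2 remote and 0.79 with 4. Dropping one uncalibrated pair therefore costs about as much power as keeping it with an opposing 1% offset, and less than keeping it with a larger one.

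**The case against.** The strongest reply is that this is an exception in a small safety study. Participants are expected at BCM, the remote route needs a specific reason, and only an attempt is promised. The text does not say that DXA will be done remotely; a missed scan is equally compatible with it. The expected frequency is not given. BMD is secondary, and no primary outcome uses DXA. All of this stands and limits the weight of the point. It does not close the gap, because nothing excludes DXA from the allowance and nothing says what to do with a remote value.

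Several stronger readings do not hold:

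- A reader might infer that the test would compare two scanners in place of before and after. It would not: a relocated pair carries treatment change plus scanner difference, and pairs scanned at BCM are untouched by this clause.
- A reader might infer that one remote scan could manufacture a positive finding. Step 3 shows that it does not raise type I error.
- It is tempting to say that travel is most likely to fail at the exit visit. The documents give no basis for that, and the point does not need it.
- Local interpretation by site investigators does not establish that a remote facility would read its own scan.

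For lung function, the American Thoracic Society requirement covers part of the problem. For pQCT, section 6 names no test, so the concern there is the reported change.

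**Conclusion.** The gap is real and modest. The plan fixes the baseline device location, lets the only later measurement move, and applies an uncontrolled paired comparison with no rule for a changed device. One remote scan shifts the mean percent change by 0.13–0.63 points at n = 8 or 0.25–1.25 at n = 4, if scanners differ by 1–5%. The main harm is to the estimate and to power. Type I error rises materially only with several remote scans whose offsets share a direction, for example to about 0.13 with 4 of 8 remote, a 2% offset and SD 2%.

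The offset, SD, true change, pooling and 5% level are all assumptions, and the frequency of remote scans is unknown. That the allowance reaches the exit DXA without a device condition rests on the text alone. The safety and pharmacokinetic conclusions do not depend on it.

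**What to change.** In sections 4.7, 4.8 and 4.9, exempt exit DXA and pQCT from the remote option, and lung function where feasible. Require the baseline device, and allow a wider window for that measurement alone if travel is delayed. Record the device identifier at each scan.

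In section 6, limit the main paired BMD analysis to pairs from the same device or with a documented cross-calibration. List any other values, and show a sensitivity analysis that includes them, so that no data are discarded.

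The cost is a few sentences of protocol and analysis wording and no extra participants. The downside is a later scan or an occasional missing pair; for one pair lost of 8, power for an assumed 3% change with SD 2% goes from 0.92 to 0.88. This is a cheap improvement.
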